8.1.3 Change from Baseline in eGFR to FU1 and FU2

This secondary endpoint pertains to Type B cohort subjects only.

The change from baseline in eGFR (baseline value is defined as the mean of Screening and Day 1 values) will be descriptively summarized by visit with central and local versions combined.

The proportion of subjects with a percent decline in eGFR from baseline to FU2 of >=20%, >=30% and >=40% will be summarized along with their 2-sided Clopper–Pearson 95% CIs. In addition, these proportions will also be summarized for all visits.

8.1.4 Change from Baseline in Daily Prednisone Dose and Cumulative Prednisone Dose Through FU1 and Through FU2

This secondary endpoint pertains to Type B subjects only.

Mean daily systemic prednisone equivalent steroid use (mg/day) and change from baseline in Type B subjects will be summarized descriptively by study windows

The proportion of subjects (with the 2-sided 95% Clopper-Pearson CI) with a prednisone daily dose equivalent < 10.0 mg/day, < 7.5 mg/day and < 5.0 mg/day

will be summarized.

Cumulative prednisone dose is computed as the total dose taken during the analysis period (Day 1 through a certain analysis visit). The cumulative prednisone dose will be summarized descriptively.

8.1.5 Change from Baseline in SLEDAI-2K scores to FU2

SLEDAI-2K is a 24 items questionnaire measuring SLE disease activity within the last 10 days. The total score is calculated as the total of presence of any of the 24 clinical and laboratory variables, weighted by the type of manifestation. The total SLEDAI-2K score ranges between 0 and 105, with higher scores representing higher disease activity. The total score is the sum of the scores assigned to each item manifestation that was present.

The change in SLEDAI-2K scores from baseline (Type A Cohort subjects) and the change from baseline (Type B subjects) will be summarized in both continuous and binary scale (e.g., decrease from baseline of > 4 or \leq 4 points) by visit. For binary scale changes the 95% CI will be calculated using the Clopper-Pearson method.

A sensitivity analysis of the change in SLEDAI-2K scores from baseline will be provided for Type B subjects. For the sensitivity analysis, values collected >56 days after the last treatment date, or after a subject received new immunosuppressive or other treatments for LN, or after subject had an increase in glucocorticoids are not included.

8.1.6 Proportion of subjects who meet the definition of complete response and partial response in their apLN at FU2

This secondary endpoint pertains to Type B subjects only.

The proportion of subjects achieving a complete and partial renal response as defined in Table 9 based on UPCR derived from a 24-hour urine collection will be summarized along with the 2-sided 95% Clopper–Pearson CI. Time to earliest complete response and time to earliest partial response will be summarized using the Kaplan-Meier method. For both analyses, subjects who have not had a response at the end of participation will be censored on the date of end of participation.

Rescue medications for lupus are defined as new immunosuppressive medications or biologic agents for lupus started prior to the endpoint evaluation. A confirmed decrease in eGFR is defined by a \geq 20% decrease from baseline at FU2 (or the last available eGFR prior to the FU2 visit if no value is available at FU2) and a \geq 20% decrease at the immediately preceding central lab eGFR.

The proportion of subjects with a complete and partial renal response will also be reported at FU4 using analogous definitions (i.e. confirmed decrease in eGFR will be based on values at FU4 and the immediately preceding eGFR).

8.1.8 Changes in FACIT-F, Fatigue Scale Score and SF-36 Domain Scores and Two Component Scores from Baseline to FU1 and FU2

SF-36 endpoint pertains to Type B subjects only. The FACIT-F endpoint pertains to Type A and Type B cohort subjects.

FACIT-F

The FACIT-F Additional Concerns Domain (also known as the fatigue subscale, FS) is a 13 item questionnaire measuring patient's fatigue level. Questionnaire has a 5-point Likert scale response format (0=all the time, 1=a little bit, 2=somewhat, 3=quite a bit, and 4=very much). In the eCRF, the score is recorded using a 1 to 5 scale, thus the actual score associated with a response will be derived by subtracting 1 from eCRF recorded values. FACIT-F score is the mean of all answered items scores, multiplied by 13, with all negatively worded item (Items 1-6, and items 9-13) scores reversed by subtracting from 4 prior to summation. FACIT-F score ranges from 0 to 52, with high scores representing less fatigue contributing to better health.

The change scores in FACIT-F, FS scale from baseline to each post-baseline assessment visit will be summarized descriptively by EQ001 dose group when applicable. In addition, number and percentage of subjects with an improvement (i.e., an increase) in FACIT-F, FS score from baseline of \geq 3 and >4 points will be summarized at each post-baseline assessment visit with 2-sided 95% Clopper-Pearson CI.

SF-36

The SF-36 is a multi-purpose, health survey with 36 questions. It yields an 8-scale profile of functional health and well-being scores as well as psychometrically based physical and mental health summary measures. SF-36 questionnaire responses at each visit for each subject will be scored for the eight health domain scale scores (Physical Functioning Scale, Role Physical Scale, Bodily Pain Scale, General Health Scale, Vitality Scale, Social Functioning Scale, Role Emotional Scale, Mental Health Scale) and the two summary component scores [Physical Component Summary Measure (PCS), Mental Component Summary Measure (MCS)] by Optum. Optum will provide both general population norm based scores and original 0-100 scores. Norm based scores of the 8 health domain scores and the two component summary scores will be summarized descriptively by visit.

8.1.9 Change from baseline in the Lupus Quality of Life (QoL), patient global assessment, and physician global assessment (PGA) to FU2

This secondary endpoint pertains to Type B subjects only.

The Lupus QoL is a 34 items questionnaire that measures disease-specific health-related quality of life (HRQoL) in adult with SLE. Individual subscales include the following: physical health (8 items), emotional health (6 items), body image (5 items), pain (3 items), planning (3 items), fatigue (4 items), intimate relationships (2 items), and burden to others (3 items). Questionnaire responses to each item has a 5-point Likert response format (0=all the time, 1=most of the time, 2=a good bit of the time, 3=occasionally, and 4=never). The mean raw domain score is transformed to scores ranging from 0 (worst HRQoL) to 100 (best HRQoL) by dividing the raw domain score by 4 and then multiplying by 100. The result represents the transformed score for that domain. The transformed domain scores are obtainable when at least 50% of the items are answered. The mean raw domain score is then calculated by totaling the item response is treated as unanswered and the domain score is calculated as indicated above. The questions for each subscale include:

- Physical health: items 1–8;
- Pain: Items 9–11;
- Planning: Items 12–14;
- Intimate relationships: Items 15 and 16;
- Burden to others: Items 17–19;
- Emotional health: Items 20–25;
- Body image: Items 26–30;
- Fatigue: Items 31–34.

The changes in each domain scores in Lupus QoL, patient global assessment and PGA scores from baseline will be summarized in both continuous and binary scale (e.g., at least 1 point improvement vs no improvement or worsened). The 95% Clopper-Pearson confidence intervals will be provided for the percent of subjects with at least 1 point improvement.

including neutralizing antibodies (NAB)], will be measured

PK parameters will be analyzed using the PK

population which is defined as subjects in the Safety Population who have at least one measurable post-EQ001 exposure serum concentration.

ADA (NAB) data will be analyzed by the Safety Population.

9.1 PK

EQ001 serum concentrations will be measured for Type A subjects

PK samples will be collected prior to study drug administration on dosing days. EQ001 serum concentrations will be analyzed using the PK Population and descriptive statistics will be provided by visit by treatment group and in each Type A and Type B cohort separately. A by-subject listing for EQ001 serum concentrations will also be provided.

9.3 Anti-drug antibody (ADA)

Serum from available timepoints will be analyzed for detection of anti-drug antibodies (ADA) against EQ001. A NAB assay will be performed on the same samples, if required. ADA sampling may be requested by the

Sponsor at an unscheduled visit to further evaluate safety in individual subjects. ADA and neutralizing ADA results will be presented in a by-subject listing for the Safety Population with Type A and Type B combined.

10 Safety

All safety analyses will be performed using the Safety Population.

10.1 Extent of Exposure

All subjects start with dose level of 1.6 mg/kg but allowed to change the dose level to 0.8 mg/kg. Dose level administrated at each visit will be summarized. Treatment exposure will be determined by overall duration of treatment and duration at each dose level. In addition, measures of extent of exposure at each dose level include the screening weight normalized average dose of study drug (mg/kg) administered, total dose of study drug (mg/kg) administered, and the number of doses administered per subject.

The duration of exposure in weeks is defined as the (last dose date - first dose date + 1)/7.

eCRFs captures the volume of EQ001 prepared and volume administered at each dosing visit. As described in the Pharmacy Manual, volume prepared at a dosing visit is based on the subject's weight (kg) and the randomized dose level (mg/kg); i.e., volume prepared (mL) = weight x dose level /100. The weight at screening is used to calculate the study drug dose, unless there has been a weight change of 20% or more from the screening weight, then the weight at visit is used.

The screening weight normalized average dose of study drug (mg/kg) administered at a dosing visit = total volume of study drug administered at all dosing visits (mL) x (100 mg/1 mL)/ (the screening weight x number of doses administered).

Duration of exposure and screening weight normalized average dose of study drug administered per dose will be summarized by continuous summary statistics (n, mean, standard deviation (SD), median, minimum, and maximum). The number and percentage of doses administered will be summarized by treatment group in each Type A and Type B cohort separately.

Cumulative volume administered will also be summarized by continuous summary statistics by treatment group in each Type A and Type B cohort separately.

10.2 Treatment Compliance

Overall treatment compliance will be calculated based on the cumulative volume of study drug administered (ml) and the cumulative volume of study drug prepared (ml).

Compliance (%) = 100 x (cumulative volume of drug administered / cumulative volume of drug prepared).

Treatment compliance will be summarized by continuous summary statistics (n, mean, standard deviation (SD), median, minimum, and maximum) by treatment group in each Type A and Type B cohort separately.

A by-subject listing of exposure and compliance data will also be created.

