 - b. **Type B Cohort**: The Follow-up Period for Cohort B subjects will end approximately 12 weeks after the last dose of study drug (Section 5.4)

Note: Contraception requirements must be continued for 130 days after the last dose of study drug for Type A and B Cohorts.

Written informed consent for study participation may be obtained up to 4 weeks prior to the Screening Visit for Type A Cohort subjects and 8 weeks prior to the Screening Visit for Type B Cohort subjects. Evaluation of eligibility will be based on laboratory results, medical history, concomitant and prior medications, vital signs, 12-lead ECG, physical examination, pregnancy testing (if applicable), and, in Type B Cohort, renal biopsy results.

Subjects will be evaluated for eligibility to receive the next dose based on laboratory and clinical criteria prior to each dose. The pre-dose laboratory evaluations may be performed at a local or central laboratory up to 14- days prior to the next target dosing day or on the target dosing day. If a subject discontinues study drug treatment prior to the last dose, they will be asked to return to the clinical study site to complete all follow up visits, as described in the SOE.

If a subject withdraws from the study, they should complete an Early Termination Visit.

added based on emerging data to meet the objectives of the study.

Inclusion Criteria:

Type A Cohort Inclusion Criteria. Subjects will be required to meet all of the following inclusion criteria in order to be eligible for study enrollment:

1. Is male or female, age \geq 18 and \leq 75 years

3. Has previously been documented to have met or currently meets Systemic Lupus International Collaborating Clinics (SLICC) and/or American College of Rheumatology (ACR) criteria for SLE

[figure not shown]
4. Received at least 1 immunosuppressive or immunomodulatory treatment (including antimalarials) for SLE at any time in the past or currently

6. Has documented elevation of antinuclear antibodies (ANA) in the past or during Screening

[figure not shown]
7. Restricted SLE treatments (e.g., other immunosuppressive medications, glucocorticoids, and antimalarials) are stable and/or washed out at Screening

[figure not shown]
8. Changes in SLE drug treatment(s), including increased doses of glucocorticoids or other SLE treatments, are not anticipated during the study

9. During Screening, has adequate hematologic function

Page 15 of 110

[figure not shown]

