10.5 Study Drug Administration

EQ001 doses will be administered at the study site by a qualified staff member and the time of injection will be recorded; subjects will be observed for a minimum of 30 minutes after administration of the study drug. Study drug will be administered via SC injection into the abdomen.

In Type A Cohorts, study drug will be administered SC every 2 weeks for 4 weeks (a total of 2 doses). The first dose level to be studied, Dose Level 1, will be 0.4 mg/kg and the maximum dose level to be studied will be 3.2 mg/kg. Intermediate dose levels are currently anticipated to be 0.8, 1.6, and 2.4 mg/kg, but other intermediate doses or doses lower than 0.4 mg/kg may be chosen

Equillium, Inc.	Clinical Study Protocol No. EQ001-19-002	Page 59 of 110
Equilium, me.	Cimical Study 110tocol 110. EQ001 17 002	1 uge 37 01 110

The dose level planned for the Type B Cohort is 1.6 mg/kg. Study drug will be administered SC every 2 weeks for 24 weeks (a total of 13 doses). This dose has been determined to not have exceeded the MTD in a Type A Cohort.

Equillium, Inc.	Clinical Study Protocol No. EQ001-19-002	Page 60 of 110
 		
7 Management	of injection-site and hypersensitivity reactions	
G		

For this study, in which the study drug will be administered SC, injection-related reactions are defined as acute onset of an illness (other than those limited to the injection-site, which are described in Section 8.3.3.2 occurring within 48 hours of study drug administration that is otherwise unexplained (e.g., by an intercurrent event or the subject's medical history) but does not

Equillium, Inc.	Clinical Study Protocol No. EQ001-19-002	Page 61 of 110
-----------------	--	----------------

meet the definition of anaphylaxis Signs of a possible injection-related reaction include fever, chills, pruritus, urticaria, chest pain, dyspnea, hypotension, and hypertension.

As clinically indicated, subjects may be treated for the reaction with antihistamines (H1 \pm H2 blocker), glucocorticoids, supportive care, and any additional interventions. Subjects with Grade 1 or 2 reactions may continue treatment with study drug with prophylactic measures such as acetaminophen, NSAIDs, H1 or H2 blockers prior to each injection. The investigator and Medical Monitor should discuss and agree on a plan for prophylaxis for future doses. Grade 3 or higher-grade reactions require permanent discontinuation of study drug treatment.

Anaphylaxis

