11 STUDY PROCEDURES

The following assessments will be conducted during screening and at the time points specified in the Schedule of Events (SOE) (Section 5.2, Section 5.3, and Section 5.4) and protocol Section 10. All missed visits must be documented in the subject's medical record and the appropriate eCRF.

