7.1 Subject Disposition

Subject disposition data will be summarized using the Safety Population. This summary will include the number and percent of subjects in each of the analysis populations (Safety, Efficacy, PK and PD), subjects completing treatment and study, and subjects discontinuing treatment and discontinuing the study by the primary reason for discontinuation. Study completion is defined by completion of the last scheduled study visit (i.e. The FU2 for Type A subjects and the FU4 visit for Type B subjects), even if some earlier visits were missed. Continuous summary statistics will be presented for follow-up duration, where the follow-up duration in weeks will be calculated as:

Follow-up duration (weeks) = (date of last contact – date of first dose of study drug + 1) / 7, rounded to 1 decimal place.

The number of subjects enrolled and by site, and the number and percent of subjects who failed screening, along with the reasons for screen failure will be presented for all subjects who signed informed consent. By-subject listings will also be created for disposition data.

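### SAP 10.2 compliance measures only how fully drawn-up doses were injected; a scheduled dose skipped before preparation does not lower it

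*SAP*

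**What the plan says.** SAP 10.2 gives one formula for overall compliance: "Compliance (%) = 100 x (cumulative volume of drug administered / cumulative volume of drug prepared". It is summarized as a continuous variable for each cohort, with a subject-level listing that shows exposure next to compliance.

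On the source of the two volumes, SAP 10.1 says "eCRFs captures the volume of EQ001 prepared and volume administered at each dosing visit". The prepared volume follows from weight and dose level. Neither section brings in scheduled doses or scheduled volume, and neither gives a rule for a dosing visit that did not take place.

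SAP 10.1 also plans several exposure summaries: duration, total dose, dose level at each visit, doses per subject, and an average dose whose divisor is "the screening weight x number of doses administered". It adds that "The number and percentage of doses administered will be summarized by treatment group in each Type A and Type B cohort separately", without saying what the percentage is a percentage of.

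The documents foresee gaps in dosing. SAP 7.1 counts a subject as completing the study "even if some earlier visits were missed". Protocol 11 says "All missed visits must be documented". The Protocol 5.1 synopsis provides for follow-up "If a subject discontinues study drug treatment prior to the last dose". Injections are not self-administered: "EQ001 doses will be administered at the study site by a qualified staff member" (Protocol 10.5).

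**The concern.** Staff draw up and give every dose at the site, so a prepared dose will nearly always be injected in full. A ratio of injected to prepared volume will therefore sit at or near 100% for almost everyone. The event that a compliance figure is normally read for, a scheduled dose that was not given, leaves both terms unchanged when nothing was drawn up.

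The figure is also inconsistent. The same missed dose lowers it if the syringe had already been prepared and was discarded, but not if the subject stayed away.

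What is at stake is how Type B is read. Thirteen doses over 24 weeks leave room for missed interim visits, and a reader may use the compliance line to judge how closely subjects followed that schedule. A subject could be listed with 10 doses and 100% compliance side by side.

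**Working it through.** The plan states no compliance figure, so there is none to reproduce. The formula is applied directly.

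**Inputs**
- Scheduled doses: 13 for Type B and 2 for Type A (Protocol 5.1; SAP 3.2).
- Prepared volume per dose (mL): weight × dose level / 100 (SAP 10.1).
- Dose level: 1.6 mg/kg in Type B.
- Assumptions: constant weight, each prepared dose fully injected unless stated, and nothing recorded as prepared for a visit that did not happen.
- Weight is not given in the documents. 60 kg is used below, and it cancels from the ratio.

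**One subject, three interim visits missed, 10 doses given**
- Volume per dose: 60 × 1.6 / 100 = 0.96 mL.
- SAP 10.2: 100 × (10 × 0.96) / (10 × 0.96) = 100%.
- Against schedule: 100 × (10 × 0.96) / (13 × 0.96) = 100 × 10/13 = 76.9%.

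**One dose missed, 12 given**
- Never drawn up: 100 × 12/12 = 100%.
- Drawn up and discarded: 100 × 12/13 = 92.3%.

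**Cohort of 20, m subjects each missing three interim doses, the rest fully dosed** (m is an assumed range). The mean under SAP 10.2 is 100% throughout. Against schedule it is [m × 76.92 + (20 − m) × 100] / 20:

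| m | SAP 10.2 mean | Doses given / scheduled |
|---|---|---|
| 2 | 100% | 97.7% |
| 5 | 100% | 94.2% |
| 8 | 100% | 90.8% |

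**Which other planned summaries show the three missed doses?**
- Number of doses: 10 rather than 13, so yes.
- Total dose: 10 × 1.6 = 16.0 mg/kg rather than 13 × 1.6 = 20.8 mg/kg, so yes.
- Average dose per administration: 10 × 1.6 / 10 = 1.6 mg/kg, unchanged.
- Duration, if the Day 169 dose was given: (169 − 1 + 1) / 7 = 24.1 weeks, unchanged.

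**What a dose count alone would miss**
- Step-down to 0.8 mg/kg after dose 3, all 13 doses given: 13/13 = 100% by count. By volume it is (3 × 1.6 + 10 × 0.8) / (13 × 1.6) = 12.8/20.8 = 61.5% of the planned amount.
- Three doses, one of them half injected: 3/3 = 100% by count. The present ratio gives 2.5/3 = 83.3%.

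The replacement therefore has to sit beside the existing ratio and the dose-level summary, not displace them.

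**The case against.** The strongest reply is that this is a matter of labelling. SAP 10.1 already plans dose counts, total dose and dose level by visit. SAP 7.1 reports treatment completion and discontinuation by reason, and Protocol 13.4 tabulates major deviations. No visible analysis population depends on compliance, SAP 6.1 rules out formal testing, and the formula is printed in full. All of this stands, and it keeps the point small. It does not make the label accurate. The dose percentage in SAP 10.1 cannot stand in for compliance while its denominator is unstated.

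A reader might go further and cite a subject who stops after 3 of 13 doses and still scores 100%, where 3/13 is 23.1%. The documents do not support calling that a compliance error. Protocol 10.7 requires permanent discontinuation after a Grade 3 or higher reaction or drug-related anaphylaxis, and Protocol 5.1 requires an eligibility check before each dose. A subject stopped or held under those rules followed the protocol. Early stopping belongs under exposure and disposition, where the SAP reports it; duration would be (29 − 1 + 1)/7 = 4.1 weeks against 24.1.

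It is also fair that some text cannot be seen (SAP 3.6, the part of the Protocol between 10.5 and 10.7, and the Pharmacy Manual). How a missed visit is recorded is therefore partly an inference from SAP 10.1.

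**Conclusion.** The concern holds as a minor correction. As written, SAP 10.2 reports how completely drawn-up doses were injected and calls it treatment compliance. Missed interim dosing visits do not lower it: 10 of 13 doses scores 100% instead of 76.9%. The per-subject result needs only that each prepared dose was fully injected and that nothing was recorded as prepared at a missed visit. The cohort means of 97.7%, 94.2% and 90.8% also rest on assumed numbers of subjects missing three doses.

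A reader might infer that missed doses are concealed or that results are biased. Neither follows. The dose count and total dose show the missed doses, and no adverse-event, laboratory or efficacy estimate uses the compliance figure. The practical effect falls mainly on the Type B final analysis, because SAP 2.2 says the Type A data have already been frozen and analysed.

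**What to change.** 1. In SAP 10.2, define compliance (%) as 100 × doses administered / doses scheduled up to treatment discontinuation or completion. Identify doses withheld under protocol rules separately, so that a required hold is not read as non-compliance.
2. In SAP 10.1, state that the percentage of doses administered uses the full planned course (13 for Type B, 2 for Type A). Present it as exposure, not compliance.
3. Keep the present ratio, relabelled for example *percent of prepared volume injected*, since it is the measure that detects partial injections.
4. Keep the dose-level-by-visit summary, and state that a dose lowered to 0.8 mg/kg counts as given, so that step-downs are read from that table.

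The cost is one new formula, one stated denominator and one changed label. The dose counts are already needed for SAP 10.1, and the schedule is fixed. One item to check is whether the eCRF records why a dose was not given. The visible text requires missed visits to be documented but does not mention a reason. Reported compliance will be lower wherever interim doses were missed.
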